4.2 Exclusion criteria

Medical conditions

1. Patients with folic acid deficiency, defined as folate <7 ng/mL, or those taking folic acid supplementation within 30 days of olaparib initiation.
2. Other malignancy unless curatively treated with no evidence of disease for ≥ 5 years except: adequately treated non-melanoma skin cancer, curatively treated in situ cancer of the cervix, ductal carcinoma in situ (DCIS), Stage 1, grade 1 endometrial carcinoma. Patients with a history of localised triple negative breast cancer may be eligible, provided they completed their adjuvant chemotherapy more than three years prior to registration, and that the patient remains free of recurrent or metastatic disease
3. Persistent toxicities (>Common Terminology Criteria for Adverse Event (CTCAE) grade 2) caused by previous cancer therapy, excluding alopecia.
4. Patients with myelodysplastic syndrome/acute myeloid leukaemia or with features suggestive of MDS/AML.

Clinical Study Protocol - 6
Olaparib - ESR-18-13807

5. Patients with symptomatic uncontrolled brain metastases. A scan to confirm the absence of brain metastases is not required. The patient can receive a stable dose of corticosteroids before and during the study as long as these were started at least 4 weeks prior to treatment. Patients with spinal cord compression unless considered to have received definitive treatment for this and evidence of clinically stable disease for 28 days.
6. Patients considered a poor medical risk due to a serious, uncontrolled medical disorder, non-malignant systemic disease or active, uncontrolled infection. Examples include, but are not limited to, uncontrolled ventricular arrhythmia, recent (within 3 months) myocardial infarction, uncontrolled major seizure disorder, unstable spinal cord compression, superior vena cava syndrome, extensive interstitial bilateral lung disease on High Resolution Computed Tomography (HRCT) scan or any psychiatric disorder that prohibits obtaining informed consent.
7. Patients unable to swallow orally administered medication and patients with gastrointestinal disorders likely to interfere with absorption of the study medication.
8. Immunocompromised patients, e.g., patients who are known to be serologically positive for human immunodeficiency virus (HIV).
9. Patients with known active hepatitis (i.e. Hepatitis B or C).
 - Active hepatitis B virus (HBV) is defined by a known positive HBV surface antigen (HBsAg) result. Patients with a past or resolved HBV infection (defined as the presence of hepatitis B core antibody and absence of HBsAg) are eligible.
 - Patients positive for hepatitis C virus (HCV) antibody are eligible only if polymerase chain reaction is negative for HCV RNA.
10. Patients with the history of COVID19 are eligible only after two consecutive negative tests for COVID19.
11. Any exceptions to the eligibility criteria may be discussed with the Principal Investigator on a case by case basis.

Prior/concomitant therapy

12. Any previous treatment with PARP inhibitor, including Olaparib, are allowed.
13. Patients receiving any systemic chemotherapy or radiotherapy (except for palliative reasons) within 3 weeks prior to study treatment. Exceptions may be discussed with the Principal Investigator.

Clinical Study Protocol - 6
Olaparib - ESR-18-13807

14. Patients receiving maintenance Bevacizumab as a single agent prior to the study and /or are planning to receive concomitant Bevacizumab with Olaparib are allowed. Patients who are receiving anti-hormonal therapy or bone protecting agents are allowed. Exceptions may be discussed with the Principal Investigator.
15. Patients who start Olaparib in combination with Bevacizumab are allowed.
16. Concomitant use of known strong CYP3A inhibitors (e.g., itraconazole, telithromycin, clarithromycin, protease inhibitors boosted with ritonavir or cobicistat, indinavir, saquinavir, nelfinavir, boceprevir, telaprevir) or moderate CYP3A inhibitors (e.g., ciprofloxacin, erythromycin, diltiazem, fluconazole, verapamil). The required washout period prior to starting olaparib is 2 weeks.
17. Concomitant use of known strong (e.g., phenobarbital, enzalutamide, phenytoin, rifampicin, rifabutin, rifapentine, carbamazepine, nevirapine and St John's Wort) or moderate CYP3A inducers (e.g., bosentan, efavirenz, modafinil). The required washout period prior to starting olaparib is 5 weeks for enzalutamide or phenobarbital and 3 weeks for other agents.
18. Major surgery within 2 weeks of starting study treatment and patients must have recovered from any effects of any major surgery.
19. Previous allogenic bone marrow transplant or double umbilical cord blood transplantation (dUCBT).
20. Whole blood transfusions in the last 120 days prior to entry to the study (packed red blood cells and platelet transfusions are acceptable).

Prior/concurrent clinical study experience

21. Participation in another clinical study with an investigational product administered in the last 1 month
22. Patients with a known hypersensitivity to olaparib or any of the excipients of the product.
23. Patients with a known hypersensitivity to folic acid or any of the excipients of the product.

Other exclusions

24. Involvement in the planning and/or conduct of the study
25. Judgment by the investigator that the patient should not participate in the study if the patient is unlikely to comply with study procedures, restrictions and requirements.

Clinical Study Protocol - 6
Olaparib - ESR-18-13807

26. Previous enrolment in the present study.
27. Breast feeding women.

4.3 Lifestyle restrictions

4.3.1 Meals and dietary restrictions

It is prohibited to consume grapefruit juice, Seville oranges while on olaparib therapy.

4.3.2 Activity

Contraception

Women of childbearing potential and their partners, who are sexually active, must agree to the use of TWO highly effective forms of contraception in combination. This should be started from the signing of the informed consent and continue throughout the period of taking study treatment and for at least 1 month after last dose of study drug(s), or they must totally/truly abstain from any form of sexual intercourse .

Men who are sexually active with women of childbearing potential must also agree to the terms listed above.

For details of acceptable methods of contraception refer to Appendix B Acceptable Birth Control Methods.

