7. Eastern Cooperative Oncology Group (ECOG) performance status 0-1).
8. Patients must have a life expectancy ≥ 16 weeks.
9. Patients with measurable and non-measurable disease are eligible.
10. There is no limit on the number of prior therapy lines. Olaparib can be used in the front or a subsequent lines of therapy as well as maintenance.
11. Patients can be enrolled with the lab results outside of the Inclusion criteria range or a performance status = 2, if olaparib is recommended by their treating oncologist/physician and the olaparib Package Insert is followed for dose adjustments.

Sex

12. Female or male

Clinical Study Protocol - 6
Olaparib - ESR-18-13807

Reproduction

13. Postmenopausal or evidence of non-childbearing status for women of childbearing potential: negative urine or serum pregnancy test within 28 days of study treatment and confirmed prior to treatment on day 1.

Postmenopausal is defined as:

- Amenorrheic for 1 year or more following cessation of exogenous hormonal treatments
 - Luteinizing hormone (LH) and Follicle stimulating hormone (FSH) levels in the post-menopausal range for women under 50
 - radiation-induced oophorectomy with last menses >1 year ago
 - chemotherapy-induced menopause with >1 year interval since last menses
 - surgical sterilisation (bilateral oophorectomy or hysterectomy)
14. Advise male patients with female partners of reproductive potential or who are pregnant to use effective contraception during treatment and for 3 months following the last dose of olaparib and to not donate sperm during this time.

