Appendix B Acceptable Birth Control Methods

Olaparib is regarded as a compound with medium/high foetal risk.

Women of childbearing potential and their partners, who are sexually active, must agree to the use of TWO highly effective forms of contraception in combination [as listed below]. This should be started from the signing of the informed consent and continue throughout the period of taking study treatment and for at least 1 month after last dose of study drug(s), or they must totally/truly abstain from any form of sexual intercourse (see below).

Acceptable Non-hormonal birth control methods include:

- Total/True abstinence: When the patient refrains from any form of sexual intercourse and this is in line with their usual and/or preferred lifestyle; this must continue for the total duration of the trial and for at least 1 month after the last dose of study drug. [Periodic abstinence (e.g., calendar, ovulation, symptothermal, post-ovulation methods, or declaration of abstinence solely for the duration of a trial) and withdrawal are not acceptable methods of contraception]
- Vasectomised sexual partner PLUS male condom. With participant assurance that partner received post-vasectomy confirmation of azoospermia.
- Tubal occlusion PLUS male condom
- IUD PLUS male condom. Provided coils are copper-banded

Acceptable hormonal methods:

- Normal and low dose combined oral pills PLUS male condom
- Cerazette (desogestrel) PLUS male condom. Cerazette is currently the only highly efficacious progesterone based pill.
- Hormonal shot or injection (e.g., Depo-Provera) PLUS male condom
- Etonogestrel implants (e.g., Implanon, Norplant) PLUS male condom
- Norelgestromin / EE transdermal system PLUS male condom
- Intrauterine system [IUS] device (e.g., levonorgestrel releasing IUS -Mirena®) PLUS male condom
- Intravaginal device (e.g., EE and etonogestrel) PLUS male condom

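### Male contraception runs for 3 months after the last dose in inclusion criterion 14, but section 4.3.2 holds men to two methods and a 1-month minimum, so men may be told the shorter period

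*Combined protocol and SAP*

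**What the plan says.** Three places in the combined protocol and SAP bear on contraception for male patients.

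- **Section 4.1, inclusion criterion 14.** The instruction begins "Advise male patients with female partners of reproductive potential or who are pregnant to use effective contraception". It runs through treatment and for 3 months after the last olaparib dose, and it bars sperm donation over the same period. It gives no number of methods.
- **Section 4.3.2, Contraception.** Women of childbearing potential and their partners "must agree to the use of TWO highly effective forms of contraception in combination", starting at consent and ending no sooner than 1 month after the last dose of study drug, or else they must abstain. The next paragraph reads: "Men who are sexually active with women of childbearing potential must also agree to the terms listed above". The section then sends the reader to Appendix B for acceptable methods.
- **Appendix B.** It restates the two-method, 1-month-minimum terms and lists acceptable combinations. It has no period for male patients and does not mention sperm donation.

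None of the three refers to the others on duration, and none is given precedence.

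**The concern.** Staff who counsel a male patient, or draft material for him, from the section headed Contraception and its appendix will find only a 1-month minimum. Staff who work from the eligibility list will find 3 months and a ban on sperm donation. The same patient could be told either.

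What is at stake is the safety of partners and pregnancies. Appendix B places olaparib in the medium-to-high category for foetal risk. Men are in scope: inclusion criterion 12 admits both sexes, and section 1.4 names prostate and pancreatic cancers among the tumours studied. A wrong instruction is also unlikely to be caught later. The last scheduled visit in tables 1.1.1 A and B is 1 month after treatment, and section 6.1.1 ties adverse-event follow-up to 30 days, so the second and third months fall after that visit.

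**Working it through.** There is no computed figure in the plan to reproduce. The check is a comparison of the texts.

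| Feature | Inclusion criterion 14 | Section 4.3.2, as extended to men | Appendix B |
|---|---|---|---|
| Minimum time after last dose | 3 months | 1 month | 1 month (no separate male period) |
| Methods | Effective; number not stated | Two, highly effective, combined | Two, highly effective, combined |
| Start | During treatment | From consent | From consent |
| Clock runs from last dose of | Olaparib | Study drug(s) | Study drug(s) |
| Pregnant partners named | Yes | No | No |
| Sperm donation | Barred for the period | Not mentioned | Not mentioned |
| Force of wording | Advice | Obligation | Obligation |

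**Difference in duration.** 3 months − 1 month = 2 months.

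**Does either rule contain the other?** Take two male patients, each with a partner of childbearing potential.

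1. He uses two highly effective methods from consent and stops 1 month after the last dose. He meets section 4.3.2 and the terms of Appendix B. He does not meet inclusion criterion 14.
2. He uses one effective method during treatment and for 3 months after, and donates no sperm. He meets inclusion criterion 14 as worded. He does not meet section 4.3.2, which asks for two methods.

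So compliance with one text does not guarantee compliance with the other, in either direction.

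**Does the wording settle it?** No. The longer period is phrased as advice and the shorter one as something men must agree to, so force and length point in opposite directions. The reference point differs too: section 5 defines study treatment as olaparib and folic acid, so the last dose of study drug need not be the last dose of olaparib.

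**The case against.** The best reply is that the texts do not strictly conflict. One month is a floor, so a man who continues for 3 months satisfies the duration in both places. The sentence in section 4.3.2 says men must also agree to its terms, which can be read as adding to inclusion criterion 14. Two highly effective methods would also meet a standard of effective contraception. Appendix B is cited only for methods and speaks to women and their partners, so its 1 month may simply be the women's rule restated. The consent form, which largely governs what men are told, is not available for review and may already be correct. No expected number of men is given, and the analysis is unaffected.

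Much of this stands. The 1 month is a minimum, inclusion criterion 14 states no number of methods, Appendix B is silent on men more than it contradicts, and the consent wording and the number of men are unknown. It does not remove the problem. That all the terms can be met together does not mean a reader of section 4.3.2 will know to do so: a man who stops at 1 month has done everything that section and its appendix ask. The cumulative reading is possible, but nothing in the protocol states it.

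**Conclusion.** The concern holds. For male patients with a partner of childbearing potential, the minimum period after the last dose is 3 months in one place and 1 month in another, a gap of 2 months. The texts also differ on methods and on whether sperm donation and pregnant partners are covered.

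The conclusion is that men may be told the shorter period, not that they will be. It rests on the protocol text alone and assumes that some staff will work from section 4.3.2 or Appendix B without turning back to inclusion criterion 14. The number of men affected cannot be estimated from the document. The primary endpoint, sample size, randomisation and analysis are untouched. This is an internal inconsistency on reproductive safety that should be corrected. Which period or method standard is right is a medical question and is not judged here.

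**What to change.** Reconcile inclusion criterion 14, section 4.3.2 and Appendix B into a single statement for male patients, and have the other two places refer to it. The statement should settle:

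- the duration after the last dose, and the last dose of which drug;
- the number and standard of methods;
- when the requirement starts;
- whether pregnant partners are covered;
- whether sperm donation is barred, and for how long.

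The medical team decides the content of each. The consent form and any counselling material should then be checked against the agreed text and changed where they differ.

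The cost is a short text amendment and possibly revised consent wording. No visit, study procedure or analysis changes.

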4.4 Screen failures

Screen failures are defined as patients who signed the informed consent form to participate in the clinical study but are not subsequently entered in the study. Minimal information includes demography, screen failure details, eligibility criteria.

Individuals who do not meet the criteria for participation in this study (screen failure) may be rescreened.

5. STUDY TREATMENTS

Study treatment is defined as any investigational product(s) (including marketed product comparator and placebo) intended to be administered to a study participant according to the study protocol. Study treatment in this study refers to olaparib and folic acid supplementation.

5.1 Treatments administered

Clinical Study Protocol - 6
 Olaparib - ESR-18-13807

Table 1 Study Treatments

	Treatment 1	Treatment 2
Study treatment name	Olaparib	Folic acid
Dosage formulation	300 mg BID	1 mg daily
Route of administration	Oral	Oral
Dosing instructions	Olaparib tablets should be taken at the same time each day, approximately 12 hours apart with one glass of water. The tablets should be swallowed whole and not chewed, crushed, dissolved or divided. Olaparib tablets can be taken with or without food.	Folic acid supplementation should be taken at the same time each day, with one glass of water. The tablets should be swallowed whole and not chewed, crushed, dissolved or divided. Can be taken with or without food.
Packaging and labelling	Study treatment will be prescribed by provider. Each container will be labelled in accordance with Good Manufacturing Practice (GMP) Annex 13 and per country regulatory requirement. Olaparib will be commercially supplied.	Study treatment will be prescribed by provider.

If vomiting occurs shortly after the olaparib or folic acid tablets are swallowed, the dose should only be replaced if all of the intact tablets can be seen and counted. Should any patient enrolled

Clinical Study Protocol - 6
Olaparib - ESR-18-13807

on the study miss a scheduled dose for whatever reason (e.g., as a result of forgetting to take the tablets or vomiting), the patient will be allowed to take the scheduled dose up to a maximum of 2 hours after that scheduled dose time. If greater than 2 hours after the scheduled dose time, the missed dose is not to be taken and the patient should take their allotted dose at the next scheduled time.

5.2 Preparation/handling/storage/accountability

The investigator or designee must confirm appropriate temperature conditions have been maintained during transit for all study treatment received and any discrepancies are reported and resolved before use of the study treatment.

Only patients enrolled in the study may receive study treatment and only authorised site staff may dispense study treatment. At site, all study treatments must be stored in a secure, environmentally controlled, and monitored (manual or automated) area in accordance with the labelled storage conditions with access limited to the investigator and authorised site staff.

The investigator, institution, or the head of the medical institution (where applicable) is responsible for study treatment accountability, reconciliation, and record maintenance (i.e., receipt, reconciliation, and final disposition records).

Further guidance and information for the final disposition of unused study treatment are provided.

5.3 Measures to minimise bias: randomisation and blinding

If a patient withdraws from the study, then his/her enrolment/randomisation code cannot be reused. Withdrawn patients will not be replaced

5.4 Treatment compliance

Patients should be given clear instructions on how and when to take their study treatment. Patients will self-administer olaparib and folic acid. Patients will be given a medication calendar to document the olaparib and (if applicable) folate doses taken. Study site staff will review the calendar monthly with the patient and discuss reasons for missed doses, if any. Patients will be instructed to notify study site personnel of missed doses.

Any change from the dosing schedule, does interruptions, dose reductions, and dose discontinuations should be recorded in eCRF.

The Investigational Product Storage Manager is responsible for managing the Investigational Medicinal Product (IMP) from receipt by the study site until the destruction or return of all

Clinical Study Protocol - 6
 Olaparib - ESR-18-13807

unused IMP. The Investigator(s) is responsible for ensuring that the patient has returned all unused IMP.

5.5 Concomitant therapy

The use of any natural/herbal products or other traditional remedies should be discouraged, but use of these products, as well as any medication or vaccine including over-the-counter or prescription medicines, vitamins, and/or herbal supplements that the patient is receiving at the time of enrolment or receives during the study must be recorded along with:

- Reason for use
- Dates of administration including start and end dates
- Dosage information including dose and frequency

The information on vitamin intake will be collected at the baseline and throughout the duration of the study. Patients will be discouraged to take folate-containing vitamin supplements for at least three months after starting olaparib therapy. However, if they have been on them before the enrolment and decline holding them, they are still eligible to participate.

Anti-emetics/Anti-diarrheals

From screening onwards, should a patient develop nausea, vomiting and / or diarrhea, then these symptoms should be reported as AEs (see Section 8.3) and appropriate treatment of the event given.

Medications that may NOT be administered

Table 2 Prohibited medications

Prohibited medication/class of drug:	
Anticancer therapy:	Not permitted while the patient is receiving study medication
Chemotherapy	
Immunotherapy	
Radiotherapy (except palliative)	
Biological therapy	
Other novel agents	

*Hormone Replacement Therapy (HRT) is acceptable

Clinical Study Protocol - 6
 Olaparib - ESR-18-13807

*Anti-hormonal agents such as aromatase inhibitors are acceptable.

Restricted concomitant medications

Table 3 Restricted concomitant medications

Medication/class of drug:	Usage (including limits for duration permitted and special situations in which it’s allowed):

Strong CYP3A inhibitors:
 
itraconazole, telithromycin, clarithromycin, boosted protease inhibitors, indinavir, saquinavir, nelfinavir, boceprevir, telaprevir
	
Strong or moderate CYP3A inhibitors should not be taken with olaparib. If there is no suitable alternative concomitant medication then the dose of olaparib should be reduced for the period of concomitant administration. The dose reduction of olaparib should be recorded in the CRF with the reason documented as concomitant CYP3A inhibitor use.


Moderate CYP3A inhibitors:
 
ciprofloxacin, erythromycin, diltiazem, fluconazole, verapamil
	
 • Strong CYP3A inhibitors – reduce the dose of olaparib to 100 mg twice daily for the duration of concomitant therapy with the strong inhibitor and for 5 half-lives afterwards. • Moderate CYP3A inhibitors - reduce the dose of olaparib to 150 mg twice daily for the duration of concomitant therapy with the moderate inhibitor and for 3 half-lives afterwards. • After the washout of the inhibitor is complete, the olaparib dose can be re-escalated.

Table 3 Restricted concomitant medications

Medication/class of drug:	Usage (including limits for duration permitted and special situations in which it's allowed):

Strong inducers:
 
phenobarbital, phenytoin, rifampicin, rifabutin, rifapentine, carbamazepine, nevirapine, enzalutamide and St John's Wort
	
Strong or moderate CYP3A inducers should not be taken with olaparib.
 
If the use of any strong or moderate CYP3A inducers are considered necessary for the patient's safety and welfare this could diminish the clinical efficacy of olaparib.

Moderate CYP3A inducers:
 
bosentan, efavirenz and modafinil
	
If a patient requires use of a strong or moderate CYP3A inducer then they must be monitored carefully for any change in efficacy of olaparib.

 • CYP3A4 substrates: hormonal contraceptive, simvastatin, cisapride, cyclosporine, ergot alkaloids, fentanyl, pimozide, sirolimus, tacrolimus and quetiapine • CYP2B6 substrates: bupropion, efavirenz • OATP1B1 substrates: bosentan, glibenclamide, repaglinide, statins and valsartan • OCT1, MATE1 and MATE2K substrates: metformin • OCT2 substrates: serum creatinine • OAT3 substrates: furosemide, methotrexate 	
Effect of olaparib on other drugs
 
Based on limited in vitro data, olaparib may increase the exposure to substrates of CYP3A4, OATP1B1, OCT1, OCT2, OAT3, MATE1 and MATE2K.
 
Based on limited in vitro data, olaparib may reduce the exposure to substrates of 2B6.
 
Caution should be observed if substrates of these isoenzymes or transporter proteins are co-administered.


Anticoagulant therapy
	
Patients who are taking warfarin may participate in this trial; however, it is recommended that international normalised ratio (INR) be monitored carefully at least once per week for the first month, then monthly if the INR is stable. Subcutaneous heparin and low molecular weight heparin are permitted.

Clinical Study Protocol - 6
Olaparib - ESR-18-13807

Table 3 Restricted concomitant medications

Medication/class of drug:	Usage (including limits for duration permitted and special situations in which it's allowed):
Palliative radiotherapy	Palliative radiotherapy may be used for the treatment of pain at the site of bony metastases that were present at baseline, provided the investigator does not feel that these are indicative of clinical disease progression during the study period. Study treatment should be discontinued for a minimum of 3 days before a patient undergoes therapeutic palliative radiation treatment. Study treatment should be restarted within 4 weeks as long as any bone marrow toxicity has recovered.
Administration of other anti-cancer agents	Patients must not receive any other concurrent anti-cancer therapy, including investigational agents, while on study treatment. Patients may continue the use of bisphosphonates or denosumab for bone disease and corticosteroids for the symptomatic control of brain metastases provided the dose is stable before and during the study and they were started at least 4 weeks prior to beginning study treatment.

